7.2.2. Secondary efficacy endpoints

Difference between the treatment arms in the proportion of completely sober patients during a 4-week period at 6 and 12 months, respectively.

The proportion of completely sober patients is measured with TLFB. To be considered sober, the patient must have entered 0 standard glasses consumed during the 4-week period preceding the 6- and 12-month visits, respectively.

The difference in the total amount of alcohol consumed per 4-week period after 6 and 12 months, respectively, compared with baseline

The total amount of alcohol consumed per 4-week period is measured in standard glasses using TLFB, and is the sum of the number of glasses for the entire period. How to determine the TLFB at baseline is stated in section 8.1.2. Follow-up TLFB is then made at each visit. The difference in the number of heavy drinking days per 4-week period at 6 and 12 months, respectively, compared with baseline

The number of heavy drinking days is measured with TLFB. Heavy drinking days are the same as days with heavy consumption, which means consumption of 4 or more standard glasses of alcohol per day for women and 5 or more standard glasses of alcohol per day for men. How to determine the TLFB at baseline is stated in section 8.1.2. Follow-up TLFB is then made at each visit.

The difference in the number of drink-free days per 4-week period at 6 and 12 months, respectively, compared with baseline.

The measuring tool becomes TLFB where the number of days of consumption specified as zero standard glass during a four-week period can be calculated. How to determine the TLFB at baseline is stated in section 8.1.2. Follow-up TLFB is then made at each visit..

The measuring tool becomes TLFB where the number of days of consumption specified as zero standard glass during a four-week period can be calculated. How to determine the TLFB at baseline is stated in section 8.1.2. Follow-up TLFB is then made at each visit.

The measuring tool becomes TLFB, where the sum of the number of standard glasses for the entire 4-week period is divided by the number of days when alcohol is consumed. How TLFB is to be determined at baseline is stated in section 8.1.2. Follow-up TLFB is then made at each visit.

Time to relapse

Depending on the goal of treatment, a relapse can be either a day of heavy consumption or drinking at least one standard glass of alcohol. Both recurrence measures will be evaluated.

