7.3.2. Alcohol calendar– Time-Line Follow-Back

Time-Line Follow-Back (TLFB) is a method that can be used to obtain information about patients' alcohol consumption. (Sobell, Maisto et al 1979). In short, it means that as far back as 3 months ago, you retrospectively reconstruct how many standard glasses you have consumed per day. It is accepted that the reporting is not an exact representation of the alcohol intake, but also that it

provides a decent benchmark, which is also sensitive to changes in the drinking pattern. An alcohol calendar (see Appendix C) is used for this purpose. For study purposes, alcohol consumption reported via TLFB is used for the 4 weeks preceding each visit. How to determine the TLFB at baseline is stated in section 8.1.2.

When filling in TLFB, the patient and therapist must consult and results of blood tests and for the intervention arm, TripleA measurements must also be taken into account to identify if and when alcohol intake has occurred.

Information about missed measurements or measurements that show alcohol in the exhaled air (both for TripleA and for regular measurements at the care provider) should be used in the TLFB call and should in the alcohol calendar correspond to a number greater than 0 standard glasses on the current day. There may be discrepancies between what the patient is willing to state in the TLFB and the information that the caregiver has available in the TripleA caregiver portal or from other sources. The caregiver should talk to the patient about this, and give the patient the opportunity to update the information in the TLFB if necessary, but should not force the patient to enter a number greater than 0 or change information provided by the patient without the patient's consent.

In CRF, it is possible for the care provider to state whether there are signs of alcohol intake that do not correspond to reported intake in TLFB.

Time: At each visit.

AUDIT (The Alcohol Use Disorders Identification Test)

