7.5.2. Loss of individual values

Missed blows are discussed with the patient during the visits. If the patient has a plausible explanation for the lack of a single puff, the caregiver can state this in the system, and indicate whether or not there should have been alcohol in the exhaled air at the time in question. A patient who so wishes may submit an extra blood sample to prove that he has been sober during the period when measurement values are missing.

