patient-reported data in TLFB form. If there are 3 positive blows in one day, it is very likely also a heavy drinking day (≥ 4 standard glasses / day for women, ≥ 5 standard glasses / day for men), which is medically serious. If there are alcohol tests performed in the evening 3 different days with just over 0.2 %, it can correspond to 2 glasses of wine for dinner - which can be completely acceptable if the goal is to reduce drinking and its somatic and psychological consequences (risk reduction). If you detect around 0.2 % in the morning 3 different days, it can be serious and very well mean 3 heavy drinking days where the alcohol consumption took place after the last alcohol test in the evening and the body did not have time to burn all alcohol before the next test in the morning.

The second thing to deal with is missed alcohol tests. These may be due to the patient being sober but for various reasons not being able to perform the alcohol test in time (not noticed the notification, flight, mobile data shadow, etc.) or relapse into alcohol consumption. Here, the patient can contact the care provider (or vice versa) and clarify what happened.

The caregiver has the opportunity to enter a new classification for an individual test in the caregiver portal, which means that the database will contain supplementary information - without overwriting the basic status. The following options are available for missed tests:

- No alcohol
- Alcohol could not be excluded
- Technical issue.

If the default status is "Alcohol could not be excluded", the following status comments can be selected:

- No alcohol
- Technical issue.

If the basic status is "Technical error", the following status comments can be selected:

- No alcohol
- Alcohol could not be excluded

The patient also has an opportunity to show that they have not had a relapse by submitting blood samples for analysis of PEth and CDT. The caregiver can then reclassify the missed alcohol tests as above.

Even if the caregiver indicates a new classification on a test performed or missed, the original data always remains, which is so that the percentage sobriety can be calculated in two ways:

- o Proportion of sober tests based on all alcohol tests performed.
- o Corrected proportion of sober tests where both performed and missed alcohol tests are taken into account, with the classification made by the care provider as above.

9.1.3.Explorative analyses

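### The calendar rule in section 7.3.2 gives a missed breath test the same default entry above 0 glasses as a positive one, even when the plan lets staff clear the miss; this can bias secondary drinking endpoints against TripleA.

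*Combined protocol and SAP*

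**What the plan says.** Section 7.3.2 governs how the alcohol calendar is completed. "Information about missed measurements or measurements that show alcohol in the exhaled air" ("both for TripleA and for regular measurements at the care provider") is to be used in the interview and "should in the alcohol calendar correspond to a number greater than 0 standard glasses on the current day". The same section then limits the rule: the caregiver raises any discrepancy but "should not force the patient to enter a number greater than 0 or change information provided by the patient without the patient's consent". Signs of intake that do not match the calendar can be noted in the CRF.

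Other sections treat a missed test differently from a positive one:

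- Section 9.1.2.2, item xvii, says of missed tests: "These may be due to the patient being sober but for various reasons not being able to perform the alcohol test in time".
- Section 7.5.2: "If the patient has a plausible explanation for the lack of a single puff, the caregiver can state this in the system". The caregiver may also indicate whether alcohol would have been present, and the patient may give an extra blood sample to show sobriety.
- Section 7.8.3.2 and item xvii allow a missed test to be given the status *No alcohol*, *Alcohol could not be excluded* or *Technical issue* in the portal. Section 7.8.3.2 also has missed tests discussed at the visit and allowed to affect the calendar answers.

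Section 7.2.2 takes sobriety from the calendar: "the patient must have entered 0 standard glasses consumed during the 4-week period preceding the 6- and 12-month visits".

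**The concern.** The default in 7.3.2 treats the absence of a measurement as evidence of drinking. Item xvii says this need not be so, and 7.5.2 and 7.8.3.2 provide a way to clear the test. That clearance is stored as a portal status, and no section carries it into the calendar. Staff who follow 7.3.2 as written would steer towards an entry above 0 on a day that the same staff have cleared.

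This differs from the detection asymmetry that section 7.8.11 acknowledges. That asymmetry concerns real drinking being found more often under frequent testing. Here an entry can be prompted when nothing was measured, and the prompt arises almost only in one arm.

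At stake are the secondary endpoints that use the calendar: completely sober patients at 6 and 12 months, sober days and total alcohol. Time to relapse is affected in part, because section 9.1.2.2 draws it from TripleA data and blood samples as well as TLFB. The completely-sober endpoint is the most sensitive, since a single day above 0 ends sober status for the whole window.

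**Working it through.** **1. Exposure.** Item xvii counts 90 tests in 30 days at 3 a day (3 × 30 = 90). Over the 28-day calendar window that is 3 × 28 = 84. Section 7.8.11 says at least 3 a day, so 84 is a minimum. Each test must be done within 60 minutes of its notification (7.6.1). The study overview (7.3.14) lists no breath tests for controls. Section 2 says breath sampling is common at the clinic, so controls may have some routine tests, but the number is not given.

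**2. Chance of at least one miss.** The documents give no miss rate, so m per test is assumed, with misses independent: P = 1 − (1 − m)^n.

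- TripleA, n = 84: 34% at m = 0.5%, 57% at 1%, 82% at 2%.
- Controls, with an assumed 1 to 4 clinic tests at m = 1%: 1% to 4%.

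**3. Chance that a truly sober patient keeps an all-zero calendar.** A miss matters only if the patient agrees to a number above 0. Let a be the share of misses so entered (assumed). Retention = (1 − m × a)^84:

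| m | a = 0 | a = 10% | a = 25% | a = 50% | a = 100% |
|---|---|---|---|---|---|
| 0.5% | 100% | 96% | 90% | 81% | 66% |
| 1% | 100% | 92% | 81% | 66% | 43% |
| 2% | 100% | 85% | 66% | 43% | 18% |

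The recorded sober proportion in the TripleA arm is the true proportion times retention. If 40% were truly sober in both arms (assumed), then at m = 1% TripleA would record 40% at a = 0, 0.40 × 0.81 = 32% at a = 25%, and 0.40 × 0.43 = 17% at a = 100%. Controls would stay close to 40%.

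**4. Sober days.** Expected days with at least one miss = 28 × (1 − (1 − m)³) = 0.42, 0.83 and 1.65 at m = 0.5%, 1% and 2%. If a quarter of those days were entered above 0, a sober patient would lose 0.10, 0.21 or 0.41 sober days per window. The mean shift is small; the all-or-nothing sober endpoint is where the effect could be large. The effect on total alcohol cannot be computed, because 7.3.2 gives no number of glasses for a missed test.

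**5. Primary endpoint.** A heavy drinking day needs 4 or more glasses (women) or 5 or more (men), per 7.2.1. An entry above 0 does not by itself create one.

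**6. Can it be undone at analysis?** The CRF field in 7.3.2 records signs of intake the patient did not report, which is the opposite case. Section 9.1.3 compares TLFB results with analyses that add blood and TripleA data; it does not remove entries prompted by a miss. Nothing marks such entries.

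**The case against.** A reader might infer that only TripleA patients can be caught by the rule, and that sober patients lose their status whenever they miss a test. The documents support neither. The sentence in 7.3.2 expressly includes clinic measurements, so the rule covers both arms and the imbalance is one of exposure. The same section forbids forcing an entry or changing the patient's answer without consent, and 7.2.2 defines sobriety by what the patient entered. A sober patient who keeps 0 remains sober.

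Other points on this side also have weight. Explained misses can be recorded, extra blood samples are offered, 7.8.11 discusses unequal detection, and 9.1.3 plans comparisons with other data sources. The rates in the illustration come from outside the documents. Independence spreads misses over the most patients, and clustering would leave more patients with none. The text is a translation, so one word such as *should* ought not to bear too much weight.

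All of this limits the size and certainty of the point but does not remove it. The no-forcing clause protects a patient who disagrees; it does not change what staff are told the calendar ought to show, and 7.8.3.2 says misses may affect the answers. The safeguards for explained misses stop at the portal. There is also a possible gap where a day is left blank. Section 9.2 sends incomplete intake data to the rules in section 8.3, apparently the present 7.3, and for TLFB the only such rule is the entry above 0. A blank day holds no patient answer for the clause to protect.

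**Conclusion.** The point holds as an unreconciled rule with an arm-differential consequence. Section 7.3.2 gives missed and positive tests the same default, without excepting misses that other sections allow to be cleared, and almost all the exposure lies in the TripleA arm. Any resulting bias runs mainly against TripleA in completely sober patients, sober days, total alcohol and, in part, time to relapse.

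Its size is unknown. It is zero if sober patients always keep 0. It could be material for the completely-sober endpoint if even a minority of misses are entered as drinking. The figures above rest on assumed miss, acceptance and sobriety rates and on independence; they show sensitivity and do not predict a result.

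A reader might also infer that the primary comparison is compromised. The documents do not support that, because an entry above 0 is not a heavy drinking day. Severity is moderate: worth correcting, but not a condition for the trial's main conclusion.

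**What to change.** Reconcile 7.3.2 with 7.5.2, 7.8.3.2 and 9.1.2.2 (item xvii):

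- Limit the default above 0 glasses to measurements that show alcohol.
- State that a missed test is discussed with the patient and given a portal status, and that the patient's own answer stands in the calendar.
- State that a miss classed *No alcohol* or *Technical issue* never prompts an entry above 0.
- Add a CRF mark for any entry above 0 prompted only by a missed test, and report the sober endpoints with and without those entries.

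The cost is a short text change, one CRF item and one added sensitivity presentation. The mark has to be in place when calendars are completed, since it cannot be reconstructed reliably later. The downside is that a missed test can hide real drinking, and some of that would go unprompted unless the patient reports it, as already happens in the control arm.

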- The number of days before the first alcohol intake (at least one standard glass) according to the patient's own information.
- The number of days before the first heavy drinking day according to the patient's own information.

Clinical Global Impression improvements after 6 and 12 months, respectively

The patients who after 12 months are "significantly improved" or "greatly improved", ie they receive a value of 1 or 2 on the CGI-I scale (see section 8.3.6) are considered to have responded to the treatment (responders). Patients with a value of 3 or higher are classified as non-responders. The proportion of responders will be compared between the treatment arms.

Change in quality of life measured with EQ-5D

EQ-5D is an accepted and widely used measure of quality of life, and the form is recommended by TLV (Dental and Pharmaceutical Benefits Agency). A general quality of life measure such as EQ-5D provides an overall picture of the study participants' perceived health, and is a good basis for health economic analyzes.

AUDIT improvement

The National Board of Health and Welfare prioritises AUDIT as a tool for identifying alcohol problems. The treatment arms will be compared with respect to:

- Proportion of patients who after 12 months have lowered their AUDIT score
- Proportion of patients who after 12 months have lowered their AUDIT score to at least one zone
- Proportion of patients who after 12 months have a risk level <II
(i.e. less than 6 AUDIT points for women, 8 AUDIT points for men).

SADD improvement

Change in alcohol dependence measured as the difference in SADD scores at 12 and 6 months, respectively, compared with baseline).

Compliance with agreed treatment

The patient remains in treatment

At each study-related visit, it is documented whether the patient remains in treatment or has interrupted his or her treatment. The proportion of patients who remain in treatment will be compared between the patient groups over time.

Compliance with TripleA

For the TripleA arm, the proportion of measurements performed compared to announced measurements will be reported. The information is retrieved from the TripleA database where all notifications and measurements are logged. Corresponding information is not available for the control arm for obvious reasons.

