7.6. Test product(s) and comparator(s)

7.6.1. Description of the exposure of the test product (s) or comparative product, if used.

The test product TripleA is used by the patients in the intervention group throughout the study period, a total of 12 months. The patient is instructed to always carry the breathalyzer and the associated mobile phone. SMS notification indicates that it is time to make a measurement. The patient then needs to complete the measurement within 60 minutes.

Measurement can not be done on the patient's own initiative, but only after activation via SMS notification. SMS notifications occur randomly several times a day, which means that the patient does not know in advance when it is time for the next measurement. The caregiver can set a break for night rest when notifications are not sent.

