7.8.3.2. Measures in the event of noted deviations in the care provider portal

Deviations in the form of a positive or missed sobriety test must be discussed with the patient at the visit and allowed to influence the TLFB responses.

The caregiver has the opportunity to enter status comments for an individual test, which means that the database will contain supplementary information - without overwriting the basic status. The following options are available:

If the basic status is "Missed", the following status comments can be selected:

- No alcohol
- Alcohol could not be excluded
- Technical issue.

If the default status is "Alcohol could not be excluded", the following status comments can be selected:

- No alcohol
- Technical issue.

If the basic status is "Technical error", the following status comments can be selected:

- No alcohol
- Alcohol could not be excluded

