9.1.2.2. Secondary efficacy endpoints

- i) Change in total amount of alcohol consumed per 4-week period after 6 months from "baseline." An ANOVA model for repeated measurements will be used to compare the groups.
- ii) Change in total amount of alcohol consumed per 4-week period after 12 months from "baseline." An ANOVA model for repeated measurements will be used to compare the groups.
- iii) Proportion of completely sober patients at 12 months A logistic regression model will be used to compare the groups.
- iv) Proportion of completely sober patients at 6 months. A logistic regression model will be used to compare the groups.
- v) Change from baseline in the number of heavy drink days per 4-week period at 6 and 12 months, respectively. An ANOVA model for repeated measurements will be used to compare the groups.
- vi) Change from "baseline" in the number of non-drinking days per 4-week period at 6 and 12 months, respectively. An ANOVA model for repeated measurements will be used to compare the groups. Förändring från "baseline" i antalet standardglas per dryckesdag per 4-veckorsperiod vid 6 och 12 månader, respektive. vii) Time to relapse (ie first alcohol intake). For

patients with the goal of becoming alcohol-free, relapse is defined as the first day after "baseline" where alcohol consumption was found, while relapse for patients with the goal of reducing alcohol consumption is defined as the first day after "baseline" where heavy alcohol consumption is found. Heavy consumption is defined for women as a day with 4 or more glasses, while for men it is defined as a day with 5 or more glasses. The data sources TripleA, TLFB or blood samples are used to detect recurrence. To compare the survival curves, ie. the variable time to recurrence, between the treatment groups a log-rank test will be used.

- vii) CGI improvement. The proportion of respondents at follow-up visits is compared between the groups with a logistic regression model.
- viii) EQ-5D. The groups are compared regarding change from "baseline" with ANOVA model. No significant difference is expected, as quality of life forms are generally not particularly sensitive to change after treatment.
- ix) Participation in treatment. To compare the survival curves, ie. the variable time until the treatment is stopped, between the treatment groups a log-rank test will be used.

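### TripleA results feed the drinking calendar and the relapse endpoint in one arm only, and Section 9 plans no analysis of these endpoints that sets them aside

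*Combined protocol and SAP*

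**What the plan says.** **Input to the calendar.** Section 7.3.2 requires blood results and, in the intervention arm, TripleA measurements to be taken into account when the TLFB calendar is completed. A missed or positive test, from TripleA or from a regular test at the care provider, "should in the alcohol calendar correspond to a number greater than 0 standard glasses on the current day". Section 7.8.3.2 adds that positive or missed TripleA tests "must be discussed with the patient at the visit and allowed to influence the TLFB responses".

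**Limits on that rule.** The caregiver should raise discrepancies with the patient "but should not force the patient to enter a number greater than 0", and may not change an entry without consent. The CRF lets the caregiver "state whether there are signs of alcohol intake that do not correspond to reported intake in TLFB". Under 7.8.3.2 a missed test can be given a status comment of no alcohol or technical issue. Under 7.5.2 the patient may offer an extra blood sample.

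**Relapse.** Section 9.1.2.2 states: "The data sources TripleA, TLFB or blood samples are used to detect recurrence". It defines relapse by treatment goal: any drinking if the goal is to be alcohol-free, a heavy drinking day if the goal is reduction. The arms are compared with a log-rank test. Section 7.2.2 defines the first of its two measures as "The number of days before the first alcohol intake (at least one standard glass) according to the patient's own information", and words the heavy-drinking measure in the same way.

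**Observation.** Section 7.3.2: "For study purposes, alcohol consumption reported via TLFB is used for the 4 weeks preceding each visit". Section 7.6.1: "The test product TripleA is used by the patients in the intervention group throughout the study period, a total of 12 months".

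**Handling.** Section 7.8.11 concedes that relapse is less likely to be detected in the control arm and that the comparison may be wrong. Section 9.1.3 sets the TLFB analyses against analyses that add blood and TripleA data.

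**The concern.** The between-arm comparison should reflect drinking, not how closely each arm is watched. Here the intervention is also a measuring device, and its readings enter the outcome by two routes.

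The first is the calendar. One entry above 0 in the 28 days makes a patient not completely sober (7.2.2), removes a sober day and adds to total intake. Section 9.1.2.2 itself accepts that a sober patient may miss a test, for example through an unnoticed notification or lost mobile coverage, although it also says a miss may be a relapse. The effect on glasses per drinking day could go either way, because an added low-intake day lowers the average.

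The second is relapse detection. If TripleA readings count directly, a relapse between visit windows can be dated in one arm and go unseen in the other.

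These endpoints carry the secondary objectives on sobriety and on fewer or later relapses (6.1.2). Unequal observation could hide a real benefit or produce apparent harm.

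**Working it through.** **1. The plan's own figure.** Section 9.2 assumes 30% against 60%, two-sided 5% and 80% power. The pooled formula gives n = [1.96·√(2·0.45·0.55) + 0.8416·√(0.21 + 0.24)]² / 0.30² = 41.97, so 42 per arm. Then 42/0.80 = 52.5, so 53 per arm and 106 in total. The sample size reproduces and is not in question.

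**2. Days observed (from the documents).** Follow-up visits are at months 1, 2, 3, 6 and 12, each with a 28-day TLFB window.
- Whole follow-up: 5 × 28 = 140 of about 365 days (38%).
- To month 3: 3 × 28 = 84 of about 91 (92%).
- After month 3: 2 × 28 = 56 of about 274 (20%), leaving 274 − 56 = 218 days outside any window.
- TripleA: about 3 × 365 = 1,095 tests per patient.

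The arms are observed similarly to month 3 and very differently afterwards. Outside the windows, controls have blood samples at visits but no daily record. Patients who leave the study are asked for their highest daily intake since last seen (9.2), but that question yields no date.

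**3. What unequal windows can do to a log-rank test (illustration).** No relapse rates are given, so these inputs are assumptions: identical drinking in both arms, 53 per arm, any drinking counted as relapse, perfect detection on observed days, blood samples ignored, and daily chance of drinking varying between patients (gamma). Controls are seen on the 140 window days, TripleA patients on every day; 500 runs per row.

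| Mean daily chance of drinking | Relapse seen, control | Relapse seen, TripleA | Rejection at nominal 5% |
|---|---|---|---|
| 1/180 | 44% | 67% | about 54% |
| 1/90 | 61% | 81% | about 43% |
| 1/30 | 83% | 92% | about 19% |

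TripleA looks worse in each row with no true difference. This models an alcohol-free goal for everyone, so it overstates the effect for a mixed population.

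**4. Missed-test rule (illustration).** The documents give neither a miss rate nor the share of misses entered as drinking. Let m be the unexcused miss rate per test and q the share entered, with 3 × 28 = 84 tests per window. For a fully sober patient, P(clean calendar) = (1 − mq)^84 and expected sober days lost = 28·[1 − (1 − mq)³]. Entries are for m = 1% / 2% / 5%.

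| q | Clean calendar, independent misses | Sober days lost | Clean calendar, misses clustered (correlation 0.05) |
|---|---|---|---|
| 0 | 100 / 100 / 100% | 0 / 0 / 0 | 100 / 100 / 100% |
| 0.05 | 96 / 92 / 81% | 0.04 / 0.08 / 0.21 | 96 / 93 / 83% |
| 0.25 | 81 / 66 / 35% | 0.2 / 0.4 / 1.0 | 87 / 75 / 48% |
| 1 (upper bound) | 43 / 18 / 1.3% | 0.8 / 1.6 / 4.0 | 72 / 52 / 19% |

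The range runs from no effect to near-total loss. It shows why q needs to be recorded; it does not estimate the bias.

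**5. Primary endpoint.** A heavy drinking day needs at least 4 glasses (women) or 5 (men). An entry above 0 does not meet that, so the rule does not act on it directly. The remaining route is prompted or more honest reporting in one arm, for which the documents give no rate.

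**The case against.** The best case for the plan has four parts.

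- **It is disclosed and partly deliberate.** Section 7.8.11 describes differential detection and gives reasons for not adding biomarker checks; 7.1.1 says the whole concept, including therapist use of the data, is under test. That stands, but disclosure is not an analysis, and the remedy needs no extra samples.
- **Section 7.2.2 rests on self-report, nominally available in both arms.** A reader might infer that no such analysis is planned at all; 7.2.2 does not support so absolute a reading. A TLFB-only relapse analysis would also equalise the windows. But the planned daily self-report is the calendar that TripleA results must inform, and 9.1.2.2 names TripleA as a source, so the sections still conflict.
- **A positive test is not always a relapse.** A reader might infer one-arm detection for every patient. Section 9.1.2.2 says evening readings just over the limit may be two glasses and acceptable under a reduction goal; it treats three positives in a day as very likely heavy drinking and morning positives only as possibly so. The direct effect is therefore clear mainly for patients with an alcohol-free goal.
- **Safeguards exist.** Consent, status comments and the optional blood sample soften the rule, and make q = 1 implausible. They do not give controls an equivalent source.

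The planned PEth/CDT comparison is arm-neutral, but it is a different endpoint, and 4.6 says PEth does not detect occasional intoxication.

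**Conclusion.** The point holds as a gap in ascertainment and in the sensitivity analyses, and should be fixed. The firm part is textual: one-arm input to the calendar (7.3.2, 7.8.3.2), conflicting relapse sources (7.2.2 against 9.1.2.2), windows covering 38% of follow-up and 20% after month 3, and a planned comparison (9.1.3) that adds TripleA data to a calendar already informed by it.

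Two further readings go too far. A reader might infer that the primary result is biased by a calculable amount; the entry rule does not create heavy drinking days, and the documents contain nothing with which to size the indirect route. A reader might also infer that the bias must run against TripleA. That is the likely direction and the one the sponsor expects, but unforced entries and caregiver reclassification leave the net direction open. The simulated rejection rates and missed-test figures rest wholly on the assumptions stated with them.

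**What to change.** 1. **Reconcile 7.2.2 and 9.1.2.2 on relapse sources**, so that the log-rank comparison does not rest on a source held for one arm, or at least add a version without TripleA. That version should use the calendar saved under item 2, the same TLFB windows in both arms and the goal-specific relapse definition. It should treat relapse as interval-censored between visits, with a discrete-time or grouped survival model. Drinking outside the windows is then unseen equally in both arms. PEth/CDT values should not count as relapse events: patients with normalized values are excluded at entry (7.7.2), and 4.6 gives PEth a half-life of 4–7 days. At 7 days, 0.5³ = 12.5% remains after three weeks and 0.5⁴ = 6.25% after four. An entry value above 0.05/0.125 = 0.4 or 0.05/0.0625 = 0.8 µmol/L would then still exceed 0.05 without any drinking. Report the planned PEth/CDT comparison alongside as support.
2. **At each follow-up visit, save the patient's calendar before TripleA results are raised**, and save the updated calendar separately. Amend 7.3.2 to allow this order. The updated calendar may remain the main analysis. The first calendar cannot be reconstructed later.
3. **Pre-specify in 9.1 two sensitivity analyses of the primary and TLFB secondary endpoints:** (a) on the calendar saved first; (b) not counting days above 0 supported only by a missed test, meaning 0 in the first calendar, above 0 in the updated one, and a missed status with no positive test that day. Describe (a) as the same collection procedure in both arms, not as common sources only: monitored patients may still report more honestly, to staff who check the portal before the visit (7.3.12).

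The cost is one extra saved calendar per follow-up visit, a CRF field and a few lines of text, with no extra samples and no change to the sample size. The sensitivity analyses set aside objective data held for one arm, and (b) may discard misses that were real relapses.
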